7.3 NCI CTCAE Definitions of Dose Limiting Adverse Events

The National Cancer Institute (NCI), Common Terminology Criteria for Adverse Events (CTCAE) will be used for monitoring adverse events throughout study including those related to dose limitation. As noted above in section 7.2, adverse events with belnacasan (VX-765/RVT-201/MSR-001) have been mild and of no consequence (grade 1 and 2 by CTCAE criteria, see below section 7.8). There is no dose escalation in this trial that could result in new symptoms though it is possible that mild symptoms may become more severe.

7.4 Pre-Existing Medical Conditions

All subjects enrolled in the study will have SARS-CoV-2 infection and at least two moderate COVID-19 symptoms or one moderate symptom and clinical evidence of moderate COVID-19. Subjects will present with high-risk for COVID-19-related inflammation, due to at least one comorbidity, including obesity, diabetes, hypertension, stable heart disease, respiratory disease, and / or non-severe fatty liver disease.

7.5 Acute Conditions Brought on by COVID-19

The development of acute kidney and/or hepatic injury has been reported as a possible complication during the disease progression of COVID-19. Acute kidney and/or hepatic injury will be addressed in the following manner depending on whether at, (1) enrollment, (2) during the study period when drug is being administered in an ambulatory setting, (3) or during admission to hospital for COVID-19 related deterioration or other illness.

1. Potential participants in this study will undergo initial screening evaluation at a MedStar site or via a home health visit which includes background laboratory testing. If the testing indicates renal failure, GFR <30 or features of acute renal failure, most notably anuria, edema on examination in a previously healthy individual, the potential participant will not be enrolled as per the inclusion criteria or otherwise clarified with the nephrology consultant managing the patient. Similarly, potential participants shown to have evidence

of elevated liver function tests (determined by ALT, AST, GGT, or ALP >2 x upper limit of normal, and/or total Bilirubin > upper limit of normal) will not be enrolled in the study.

- 2. Laboratory testing throughout the study period (see Section 5.2 Table 1) may, though unlikely, show an acute change in renal or liver testing to indicate acute organ-specific disease or involvement as a possible complication of COVID-19. In such a circumstance, subjects will be directed to seek care from the respective hospital/specialist. In the case of acute liver injury with functional impairment, the IP will be discontinued immediately after blood has been taken for future assessment of drug levels. In the case of subjects with elevated liver function tests suggestive of acute liver injury without functional impairment, IP will be held to discern in the first instance the possibility of an adverse event and restarted in consultation with the managing hepatologist if it is determined to be COVID-19 related hepatopathy. In the case of subjects with acute renal injury, IP will be held to discern in the first instance the possibility of an adverse event and restarted in consultation with the managing nephrologist if it is determined to be COVID-19 related nephropathy. DSMB guidelines for unblinding will be followed in these cases as relevant.
- 3. Acute liver and kidney injury may be seen in the face of hospital admission in patients with worsening COVID-19, in which case the patients will be managed similarly to number 2 above (also see Section 5.3 on discontinuation).

7.6 Treatment Emergent Adverse events

A treatment-emergent adverse event (TEAE) is defined as any event not present prior to the initiation of the treatments or any event already present that worsens in either intensity or frequency following the start of IP administration.

Adverse events will be captured following the first dose of IP and could be related or unrelated to the study drug. A TEAE is defined as any AE that occurs after the subject takes the first dose of IP.

Separate summaries for adverse events that occur during treatment (summary of treatment emergent adverse events) will be provided.

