7.9 Reporting Requirements

Any adverse event, defined below, that begins any time between the start of the first dose and

within 28 days after the end of the last dose are to be recorded on the appropriate CRF and in detail

in the source documentation (preferably the electronic medical record directly).

Adverse Event: Any untoward medical occurrence in a subject administered a pharmaceutical

product, which does not necessarily have to have a causal relationship with this treatment. An

adverse event can be any unfavorable sign (including an abnormal laboratory finding), symptom,

or disease temporally associated with the use of the investigational drug, whether or not considered related to the investigational drug.

Serious Adverse Event: An untoward event or reaction that at any dose:

- results in death
- is life-threatening
- results in hospitalization or prolongs existing hospitalization
- results in permanent or significant disability or incapacity
- requires intervention to prevent permanent impairment/damage
- results in congenital anomaly or birth defect

In addition, any important medical event that may not result in death, be life-threatening, or require hospitalization may be considered serious when, based upon appropriate medical judgment, they may jeopardize the patient or subject and may require medical or surgical intervention to prevent one of the outcomes listed in this definition.

Life-threatening: An event which a subject was at risk of death at the time of event. There is a distinction between the severity and the seriousness of an adverse event. Severity is a measurement of intensity, thus a severe reaction is not necessarily a serious adverse event. For example, a headache may be severe in intensity, but would not be serious unless it met one of the criteria for serious adverse events listed previously.

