7.10 Serious Adverse Events

Adverse events (AEs) and serious adverse events (SAEs) will be collected from the time the first dose of IP is administered until 28 days after the last dose of IP. Medical occurrences that began prior to the start of study treatment, but after obtaining informed consent will be captured as Medical History/Current Medical Conditions on the CRF. The Investigator or site staff will be responsible for the identification and documentation of events meeting the criteria and definition of an adverse event or serious adverse event, as provided in the study protocol. SAEs assessed as related to study participation (e.g., dosing, protocol mandated procedures, invasive tests, or change in existing therapy) or related to a concomitant medication will also be captured once the subject has taken the first dose of study medication.

In the event of an AE or SAE, it will be the responsibility of the Investigator to review all documentation (e.g., hospital progress notes, laboratory, and diagnostics reports) relative to the event and attempt to establish a diagnosis of the event based on signs, symptoms, and other clinical information. Once the Investigator becomes aware that an SAE has occurred, they are to report the information to MedStar Health within 24 hours and provide an assessment of causality.

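### Section 7.6 words the treatment-emergent rule in ways that give different counts, and Sections 7.9 and 7.10 go by when an event begins without carrying its worsening clause

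*Combined protocol and SAP*

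**What the plan says.** Section 7.6 has two sentences that define the term and a third that describes the table.

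- First definition, for new events: "A treatment-emergent adverse event (TEAE) is defined as any event not present prior to the initiation of the treatments". The same sentence goes on to include symptoms that a subject already has at entry, under this condition: "any event already present that worsens in either intensity or frequency following the start of IP administration".
- Second definition: "A TEAE is defined as any AE that occurs after the subject takes the first dose of IP". It has no worsening clause and no end date.
- Table description: "Separate summaries for adverse events that occur during treatment (summary of treatment emergent adverse events) will be provided". Dosing runs through day 28.

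Section 7.8 tells sites to enter exacerbations and disease-related events on the CRF throughout the study, and to record when an exacerbation of a pre-existing condition started. It also requires that treatment-related events have onset dates no earlier than first study treatment.

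Section 7.9 sets the recording rule: "Any adverse event, defined below, that begins any time between the start of the first dose and" a closing point, which it puts at 28 days from the final dose. Section 7.10 repeats that window and adds: "Medical occurrences that began prior to the start of study treatment, but after obtaining informed consent will be captured as Medical History/Current Medical Conditions".

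The primary endpoint (3.2) is the incidence of AEs and SAEs to day 60. Section 8.4 analyses the count by Poisson regression over 60 days from randomization. It also lists TEAEs among the events to be tabulated, without saying which wording of 7.6 applies. It does not say whether a worsened entry symptom is a countable event in the Poisson model.

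**The concern.** Two programmers could build different TEAE tables from the same data, each following a sentence in 7.6. Two site coordinators could likewise record the same patient differently: one under 7.8, which asks for exacerbations, the other under 7.9, which asks only for events that begin after the first dose.

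In many trials worsening of a baseline symptom is a side issue. Here every subject enters with COVID-19 symptoms. Headache, nausea and vomiting are on the qualifying symptom list (5.3) and among the adverse effects already reported for belnacasan (1.4). How a worsened entry symptom is handled therefore bears on known drug effects, in a trial whose primary endpoint is AEs.

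**Working it through.** The plan states no figure on this point, so there is none to reproduce. The check compares the wordings and then sizes the consequences.

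**1. Score five invented events under each wording.** The second definition can be read by onset or by presence after dosing. The during-treatment column takes new or worsened events on days 1–28.

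| Event | New or worsened | After first dose, by onset | After first dose, by presence | During treatment |
|---|---|---|---|---|
| Entry headache, worse on day 3 | yes | no | yes | yes |
| Entry vomiting, unchanged | no | no | yes | no |
| New rash, day 10 | yes | yes | yes | yes |
| New dizziness, day 45 | yes | yes | yes | no |
| New event, day 58 | yes | yes | yes | no |
| Count | 4 | 3 | 5 | 2 |

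The day-58 event falls outside the collection window of 7.9 and 7.10. Dropping it gives 3, 2, 4 and 2. The list shows that the wordings diverge; it does not estimate by how much in this trial.

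**2. Size of the window difference.** With the last dose on day 28, collection ends on day 28 + 28 = 56.

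- Constant AE rate (assumed): 56/28 = 2.0.
- If collection ran to day 60: 60/28 = 2.14.
- If 70% of AEs fell in days 1–28 (assumed): 1/0.70 = 1.43.

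The window also misses the day-60 endpoint by 60 − 56 = 4 days. If the last dose is on day 14, it ends on day 14 + 28 = 42, which is 18 days short.

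**3. Trace an entry headache that worsens on day 3.**

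- First definition in 7.6: a TEAE.
- 7.8: recorded, with the date the worsening began.
- Second definition in 7.6, by onset: not a TEAE.
- 7.9, by onset: not recorded, since the headache began before the first dose.
- 7.10, medical-history sentence: applies only if the headache began after consent and before dosing.

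Section 7.8 asks for the date of worsening but does not say that the worsening becomes a new AE with that date as its onset. If a related worsening kept its original onset date, it would also breach the onset-date rule in 7.8.

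**4. Effect on the rate ratio if worsened entry symptoms are missed.** All inputs are assumed.

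- The same share g of events lost in both arms: 2.0(1 − g)/(1 − g) = 2.0, so the ratio is unchanged. The Poisson standard error of the log ratio grows by 1/√(1 − g): 1/√0.75 = 1.15 at g = 0.25 and 1/√0.50 = 1.41 at g = 0.50.
- Only a share f of the drug-excess events lost: observed ratio = 1 + (IRR − 1)(1 − f). A true 1.6 appears as 1.45, 1.30 or 1.15 at f = 0.25, 0.50 or 0.75.
- The same absolute number lost in both arms, equal to 25% of the placebo rate: (1.6 − 0.25)/(1 − 0.25) = 1.35/0.75 = 1.80.

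The ratio can stay put, shrink or grow, depending on which events are lost. The number of events falls in every case.

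**The case against.** The strongest reply is that worsening is already covered twice: by the first definition in 7.6, and by 7.8, which orders exacerbations onto the CRF. A site that follows 7.8 records the worsened symptom with its own start date. It is lost only if 7.9, or the second definition, is read strictly by original onset and 7.8 is set aside. This largely stands: the documents create an ambiguity, not an instruction to discard these events. But 7.9 and 7.10 are the sections that set what is collected, and they omit the clause.

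A reader might infer that 7.9 and 7.10 file everything that began before dosing as medical history. The documents do not support that. Section 7.9 does not mention medical history. Section 7.10 sends there only what began between consent and first dose, usually a short interval because the Schedule of Events expects screening and day 1 to coincide in most cases. Qualifying symptoms normally predate consent.

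The primary Poisson count is of AEs and SAEs and is not limited to TEAEs, so the 2.0-fold figure concerns a descriptive table. That is correct. The table is also to be split by study period, which may give part of an on- and off-treatment split, but 8.4 does not say what the periods are. Finally, 7.6 has two definitions and a table description, not three definitions. That is also right, although the description still conflicts with both.

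**Conclusion.** The conflict is in the text and should be settled before AEs are coded. There are two separate consequences.

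The TEAE table depends on the sentence followed, by about 2.0-fold for dosing that ends on day 28 if the AE rate is constant, and by less if AEs cluster early, as is plausible in an acute illness.

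On a strict onset reading, worsened entry symptoms that are also known drug effects could be left out of the AE data behind the primary endpoint. How many is unknown, because the documents give no frequency for these symptoms at entry.

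A reader might go further and infer a bias toward no difference between arms. That would require the missed events to be enriched for drug effect, which nothing in the documents establishes; proportional loss leaves the ratio unchanged. What can be said is that events and precision would be lost, which matters with 20 subjects per arm.

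**What to change.** - **7.6:** keep one definition: an event that begins, or worsens in intensity or frequency from its level at enrollment, on or after the first dose and up to day 60. Delete the second definition and the during-treatment label.
- **7.9 and 7.10:** write *begins or worsens*, and align the collection window with the day-60 endpoint. Without this alignment, the new 7.6 wording would conflict with the present limit of 28 days after the last dose.
- **Recording:** enter a worsening as a new AE dated from the worsening.
- **8.4:** state that such an event counts in the Poisson analysis, and tabulate TEAEs up to and after the last dose separately.
- **Reference level:** record a CTCAE grade for each entry symptom at enrollment. The patient-reported scores are not CTCAE grades and cannot serve as the reference without a mapping.

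The cost is small: protocol and CRF-guideline wording, plus one baseline grading of symptoms that are already assessed at enrollment.

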7.7 Laboratory Abnormalities

Clinical labs will be performed locally at WHC or other MedStar clinical sites. Labs to be drawn during the study include serum chemistries, a hematology panel and an immune panel (see Appendix 12.1 for more details). A serum pregnancy test must be performed, and the result must be negative prior to the entry of women of child-bearing potential.

Clinical laboratory reports must be reviewed by a physician for out-of-range values within 12 hours of receipt. Out-of-range values will be evaluated using the following notations:

- NCS: Not clinically significant
- LE: Laboratory Error
- PT: Subject abnormal; relates to the subject's usual state of health
- CS: Clinically Significant. This value cannot be explained by any of the other indicators.

By definition a lab value flagged as "CS" indicates an adverse event and will be captured on the CRF. A laboratory test flagged "CS" should be repeated as soon as possible, then the Investigator should use his or her judgment as to whether the abnormal finding is sufficient reason to immediately withdraw the subject from the study.

If a laboratory value is considered to be serious and life-threatening and at least possibly related to the study drug, the subject should be immediately discontinued from the study and appropriate therapy started. Refer to Sections 7.8 to Section 7.13 for definition of a serious adverse event and related terms, and details on reporting a serious adverse event.

Particular attention will be paid to determine the possibility of drug induced liver injury (DILI) as detailed in the FDA guidance document "Drug-Induced Liver Injury: Premarketing Clinical Evaluation." Liver tests (ALT, AST, ALP, and total Bilirubin) will be performed at enrollment and at days 7, 14, and 28 throughout the drug administration period. For patients exhibiting signs of liver disease such as fatigue, nausea, vomiting, right upper quadrant pain or tenderness, fever, or rash, extensive laboratory testing will be performed that includes above liver chemistries immediately. Otherwise, on routine weekly testing an increase of serum aminotransferase levels to >3x upper limit of normal would automatically trigger repeat testing within 48 to 72 hours of all four of the usual serum measures (ALT, AST, ALP, and total Bilirubin) to confirm the abnormalities and to determine if they are increasing or decreasing. If symptoms and/or aminotransferase levels remain >3x upper limit of normal, the participant will be monitored more

closely with lab schedule, in-person or virtual evaluation twice weekly or more. A thorough evaluation for additional causes of liver test anomalies will be conducted in consultation with Hepatology. A case report form page will be created and DSMB review triggered. Otherwise, discontinuation of treatment will be considered immediately if:

- ALT or AST >8x upper limit of normal
- ALT or AST >5x upper limit of normal for more than 2 weeks
- ALT or AST >3x upper limit of normal and total Bilirubin >2x upper limit of normal or INR >1.5
- ALT or AST >3x upper limit of normal with the appearance of fatigue, nausea, vomiting, right upper quadrant pain or tenderness, fever, rash, and/or eosinophilia (>5%).

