7.8 Adverse Event Assessment and Recording

All adverse events, exacerbations of concomitant illnesses, or events known to be related to underlying disease processes or concomitant medications are to be recorded on the CRF throughout the study. If a pre-existing condition worsens during the study, the date on which the exacerbation began should be recorded. Onset dates for study treatment-related adverse events must be on or after the date of initial study treatment use.

Adverse event recording will include the date of onset, severity, duration, whether or not the study medication was discontinued because of the event, the treatment given, and the outcome. The Investigator must also assess whether the event was related to the study medication, concurrent drug therapy, underlying disease, a combination of these factors, or if it is unknown. Subjects experiencing an adverse event should be carefully followed to determine outcome.

The Investigator will use the NCI-CTCAE for adverse event monitoring, version 5.0 will be applied in all instances. CTCAE version 4.03 may also be used especially when assessing laboratory tests given the complexity in applying version 5.0 in all instances, see www.lexjansen.com/phuse-us/2020/dh/DH16.pdf

Definitions to grade the severity of the event:

Grade 1: Mild; asymptomatic or mild symptoms; clinical or diagnostic observations only; intervention not indicated.

Grade 2: Moderate; minimal, local, or non-invasive intervention indicated; limiting age-

appropriate ADL.

Grade 3: Severe or medically significant but not immediately life-threatening; hospitalization

or prolongation of hospitalization indicated; disabling; limiting self-care ADL.

Grade 4: Life-threatening consequences; urgent intervention indicated.

Grade 5: Death.

The relationship or association of the study medication in causing or contributing to the adverse event will be characterized as not related, remote, possible, probable, or definite as defined below:

• Not related: Evidence indicates no plausible direct relationship to the study medication

• **Remote:** Suggests other conditions are reasonably likely to account for the event including concurrent illness, progression or expression of the disease state, or reaction to concurrent

medication

• **Possible:** Suggests that the association of the event with the study medication is unknown;

however, the adverse event is not reasonably supported by other conditions

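### Sections 7.6, 7.7, 7.9 and 7.10 disagree on whether a laboratory abnormality carried over from before dosing is an AE, and the primary count in 8.4 does not settle it

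*Combined protocol and SAP*

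**What the plan says.** Section 7.7 gives the reviewing physician four codes for an out-of-range value: not clinically significant (NCS), laboratory error (LE), "PT: Subject abnormal; relates to the subject's usual state of health", and clinically significant (CS). CS is what remains when the others do not fit: "This value cannot be explained by any of the other indicators". Any CS value, by definition, "indicates an adverse event and will be captured on the CRF". None of the four codes refers to the pre-dose sample.

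Section 7.6 defines a TEAE twice. The first definition covers "any event not present prior to the initiation of the treatments or any event already present that worsens in either intensity or frequency". The second covers every AE after the first dose and has no baseline condition.

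Section 7.9 records AEs that begin between the first dose and 28 days after the last. Section 7.10 uses the same window and adds: "Medical occurrences that began prior to the start of study treatment, but after obtaining informed consent will be captured as Medical History".

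Section 8.4 analyses the primary endpoint by Poisson regression on counts of AEs and SAEs to 60 days from randomization and reports an IRR. It mentions TEAEs only for the descriptive summaries.

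**The concern.** Subjects enter within 7 days of symptom onset with active COVID-19. Section 3.4 lists CRP, ferritin, LDH, D-dimer and lymphocytes among the markers of COVID-19 inflammation and organ involvement, and Appendix 12.1 measures them. Abnormal values before the first dose are therefore foreseeable, and many will still be abnormal at the next draw.

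Whether such a persisting value is an AE decides whether it enters the primary count. Two staff members following different sections could code the same value differently. Events that began before treatment say nothing about harm caused by treatment. In the count they either dilute a real difference or, if the drug alters their persistence, create a difference of another kind.

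**Working it through.** **Step 1: follow one value through the text.** Take a CRP that is raised and clinically significant in the pre-dose sample, and still clinically significant but lower at day 7.

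- *Section 7.7.* It is neither a laboratory error nor the subject's ordinary health, and it is judged significant. CS is the only code left, so it is an AE.
- *Section 7.6, second definition.* Once it is an AE recorded after the first dose, it is a TEAE.
- *Section 7.6, first definition.* It was present before treatment and has not worsened, so it is not a TEAE.
- *Sections 7.9 and 7.10.* It began before the first dose, so it is medical history.
- *Section 7.8.* The onset rule, "Onset dates for study treatment-related adverse events must be on or after the date of initial study treatment use", does not decide the case. It covers only treatment-related AEs. Section 7.8 also asks for events due to underlying disease to be recorded.
- *Section 8.4.* The primary count is AE/SAE. No TEAE restriction is stated, so the conflict passes into the IRR.

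The first two rules include the value and the next two exclude it. No sentence ranks them.

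**Step 2: the plan's own figure.** Section 8.7 says that the difference in rate ratios must exceed 60% for 80% power at 5% with 20 per group. It gives no placebo event rate, so the figure cannot be reproduced exactly. The Poisson Wald formula gives the rate at which it would hold, taking 5% as two-sided:

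rate = (1.960 + 0.842)² × (1 + 1/R) / (20 × (ln R)²)

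- R = 0.40: 7.849 × 3.5 / (20 × 0.8396) = 1.64 events per placebo subject.
- R = 1.60: 7.849 × 1.625 / (20 × 0.2209) = 2.89 events per placebo subject.

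The figure is attainable, but it fixes no rate for the next step.

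**Step 3: equal carry-over in both arms.** The assumptions, none of them from the documents, are a placebo mean of 2 AEs per subject, a true IRR of 2.0, Poisson counts and full follow-up. Let m be the carried-over laboratory AEs per subject.

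- Expected IRR = (4 + m)/(2 + m).
- SE of log IRR = √(1/(20(2 + m)) + 1/(20(4 + m))).
- Power = Φ(ln IRR/SE − 1.960).

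| m | Expected IRR | SE | Power |
|---|---|---|---|
| 0 | 2.00 | 0.194 | 95% |
| 0.5 | 1.80 | 0.176 | 92% |
| 1 | 1.67 | 0.163 | 88% |
| 2 | 1.50 | 0.144 | 80% |

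The result depends on the assumed rate. With 1 AE per placebo subject and the same true IRR, power is 72% at m = 0, 60% at m = 0.5 and 39% at m = 2. Starting from the section 8.7 scenario (true IRR 1.60, 2.89 AEs per placebo subject, 80% power), m = 0.5, 1 and 2 give IRRs of 1.51, 1.45 and 1.35 and power of 75%, 71% and 62%.

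If the true IRR is 1, equal carry-over leaves it at 1.

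**Step 4: unequal carry-over.** Suppose the true IRR is 1 with 2 AEs per subject, and the drug halves the persistence of entry abnormalities. With m now the placebo carry-over, expected IRR = (2 + 0.5m)/(2 + m). For m = 0.25, 0.5, 1 and 2 this is 0.94, 0.90, 0.83 and 0.75, which is away from 1 and in the drug's favour.

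**Step 5: if 7.9 and 7.10 govern**, m = 0 and nothing changes.

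**The case against.** The strongest reply is that the protocol already has an onset rule. Sections 7.6, 7.9 and 7.10 capture AEs only from the first dose, and 8.4 counts from randomization, which follows the screening panel. A reader might infer from 7.7 that every abnormality in the screening sample is itself an AE. The documents do not support that: those values fall outside AE collection even when screening and first dose share a date. This part of the reply stands. It does not dispose of the day 7 value, which 7.7 makes an AE in its own right. Section 7.7 does not send the physician to the enrollment value or to 7.9 and 7.10.

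A reader might also infer that the PT code lets drug-caused worsening in comorbid subjects disappear. That goes too far. Section 7.8 requires exacerbations of concomitant illness to be recorded. Section 7.7 triggers repeat testing when aminotransferases exceed three times the upper limit, whatever the code. Section 8.4 tabulates every laboratory result with its change from baseline.

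Nor is the bias always toward 1. That needs equal carry-over and a true IRR other than 1, and the trial's own hypothesis is that belnacasan changes inflammatory markers.

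Finally, the safety determination in 8.4 rests on grade 4 or 5 SAEs probably related to belnacasan. The pause rule in 7.15 rests on SAEs of grade 3 or higher that are at least possibly related. Dilution of the all-AE count changes neither. Section 8.7 also concedes that power is likely to be inadequate. These points limit the consequence to the primary IRR but do not remove the conflict.

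**Conclusion.** The point holds as a conflict between rules. For abnormalities present before dosing and still clinically significant at day 7 or later, 7.7 and the second definition in 7.6 include what 7.9, 7.10 and the first definition in 7.6 exclude. Because 8.4 has no TEAE restriction, carried-over COVID-19 abnormalities can enter the primary rate ratio. The documents do not show that they will.

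The direction is conditional: toward 1 with equal carry-over and a true IRR other than 1, and possibly away from 1 if the drug changes persistence. The size cannot be computed from the documents. On the main set of assumptions the loss is modest at m = 0.5 (95% to 92%) and material at m = 2 (80%). The calculation treats counts as Poisson and does not address the negative binomial alternative that 8.4 allows.

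**What to change.** - **Section 7.7:** state that a CS value is an AE only if it is new or has worsened relative to the last pre-dose sample. CTCAE grade can guide this, with investigator judgment for clinically significant worsening within a grade. A fixed one-grade threshold is not needed and would miss such cases. Add that CS values in the pre-dose sample go to medical history, as in 7.10.
- **Section 7.6:** keep only the first TEAE definition.
- **Section 8.4:** state that the primary rate ratio counts treatment-emergent AEs and SAEs on that definition.

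The cost is a few sentences and a data-entry check against enrollment values that are already collected. The downside is that analytes with no pre-dose result need a stated default.
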